Appendix A. Power calculations

Est. # eligible, per week (7 per day to pediatrics) **35**

Est. # eligible over: 9 weeks **315**

of facilities (clusters) **63**

Cluster size **5**

Least detectable
differences

Assumptions: Power = 0.80, alpha = 0.05

For proportions, P0=0.50

ICC = 0.01 0.657

ICC = 0.03 0.663

ICC = 0.05 0.679

For proportions, P0 = 0.80

ICC = 0.01 0.912

ICC = 0.03 0.915

ICC = 0.05 0.919

Surveys	
Response rate	0.6
N	189
N per cluster	3

For means,

ICC = 0.01 0.322 0.412

ICC = 0.03 0.334 0.42

ICC = 0.05 0.346 0.427

Ref: University of Aberdeen cluster sample size calculator

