Based on initial data in the pilot period, we estimate that the message pool handlers will send the regional pharmacy team 7 secure messages for straightforward ADHD medication refill requests per weekday, i.e., 35 eligible messages per week. We estimate based on expert opinion that 30% of these patients don't have a weight check in the previous 6 months. Assuming a 9-week evaluation period, the estimated sample size is 315 patients, or an average of 5 patients in each of the 63 clusters.

Given the group-randomization study design, calculation of sample sizes and minimum detectable treatment effects must account for the expected intraclass correlation (ICC) of observations within facilities. The ICCs in outcomes of interest are expected to be small, and therefore we present minimum detectable effects for an expected ICC of .03.

For Aim 1, the primary outcome is the % of patients without a weight check in the past 6 months who received referral for an appropriate follow-up visit. The following estimates assume that 30% of the 315 patients with secure messages will have not had a weight check in the past 6

months, for a sample size of 95 (63 clusters with 1.5 patients each). We also assume a desired power of 80%, a two-tailed alpha of 0.05 and an ICC of .03. If 50% of patients in the PCP Care group will receive an appropriate referral, the least detectable difference will 77%. If 80% of the patients in the PCP Care group receive an appropriate referral, the least detectable difference will be 98%. Thus, this sample size yields good power to identify only large differences between the two arms in the primary outcome.

For Aim 2, the outcome is days from the secure message to the prescription order. The following estimates assume a sample size of 315 (63 clusters with 5 patients each), a desired power of 80%, a two-tailed alpha of 0.05 and an ICC of .03. The least detectable effect size for a comparison of means will be 0.334. In other words, this study will have good power to find a statistically significant difference between the Pharmacist Care and PCP Care groups for a small to medium effect size.

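### Appendix A computes its detectable proportions on all 315 requests and has no calculation for the 95-patient primary outcome; separately, one entry (0.679) should be 0.668

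*Combined protocol and SAP*

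**What the plan says.** Appendix A (Power calculations) prints its base above the results: "Est. # eligible over: 9 weeks 315", then "of facilities (clusters) 63" and "Cluster size 5". Under "Assumptions: Power = 0.80, alpha = 0.05" it lists detectable proportions at ICC 0.01, 0.03 and 0.05. For a comparison rate of 0.50 they are 0.657, 0.663 and 0.679 (printed as "ICC = 0.03 0.663" and "ICC = 0.05 0.679" for the last two). For a rate of 0.80 they are 0.912, 0.915 and 0.919. The rows are labelled only as proportions; no outcome is named.

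Section 4.8 (Sample size and power) takes Aim 1 to rest on the 30% of 315 patients with no weight in the previous six months, which is 95 patients or 1.5 per cluster. It sets the same error rates: "We also assume a desired power of 80%, a two-tailed alpha of 0.05 and an ICC of .03". Its result is "If 50% of patients in the PCP Care group will receive an appropriate referral, the least detectable difference will 77" (that is, 77%), and 98% where the comparison rate is 80%. It concludes that only large differences in the primary outcome can be detected with good power. Aims 2 and 3 are powered as comparisons of means.

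**The concern.** The appendix uses the same two comparison rates, the same power and alpha, and (in its middle row) the same ICC as the Aim 1 calculation in section 4.8, yet its detectable rates are much closer to the comparison rate. Since section 4.8 powers no other proportion, a reader who goes to the appendix for the support behind Aim 1 will naturally take these rows to be it. They are not, and nothing else in the appendix supports the 77% and 98%.

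What is at stake is how a null primary result is read. The abstract says that better or similar outcomes would favour continuing pharmacist management. Someone who believes the trial had 80% power for a 16-point difference will read a non-significant result as stronger evidence of similarity than 95 patients can give.

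The 0.679 entry is a separate matter. It breaks the pattern of its own column: the steps are 0.006 and then 0.016, although the design effect rises by the same amount each time.

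**Working it through.** **Inputs.** Appendix A: N = 315, 63 clusters, cluster size m = 5, power 0.80, alpha 0.05. Section 4.8: two-tailed test, ICC 0.03, primary-outcome N = 95, m = 1.5. Allocation is 32:31 facilities, taken as 1:1.

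**Formula.** Design effect D = 1 + (m − 1) × ICC. Effective size per arm n = (N/2)/D. The detectable rate p solves n = (1.960 + 0.842)² × [p0(1 − p0) + p(1 − p)]/(p − p0)², where (1.960 + 0.842)² ≈ 7.849. This is the two-proportion test with unpooled variance. The results are rates in the Pharmacist Care arm, although both places call them differences.

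**Step 1: the appendix on its own base (N = 315, m = 5).**

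| ICC | D | n per arm | p at p0 = 0.50 (printed) | p at p0 = 0.80 (printed) |
|---|---|---|---|---|
| 0.01 | 1.04 | 151.4 | 0.657 (0.657) | 0.912 (0.912) |
| 0.03 | 1.12 | 140.6 | 0.663 (0.663) | 0.915 (0.915) |
| 0.05 | 1.20 | 131.3 | **0.668 (0.679)** | 0.919 (0.919) |

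Five of six entries match to three decimals, so the base is certain: all 315 requests. The means also reproduce, as 0.322, 0.334 and 0.346 on 315, and 0.412, 0.420 and 0.427 (to within rounding) on the 189 survey responses.

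**Step 2: the odd entry.** At p = 0.668 the required n is 7.849 × 0.4718/0.168² ≈ 131.2, which agrees with 131.3. At p = 0.679 it is 7.849 × 0.4680/0.179² ≈ 114.6 per arm, or 2 × 114.6 × 1.20 ≈ 275 requests, not 315. With 315 requests, power at 0.679 is 85%. Other versions of the test give 0.670 (pooled variance), 0.670 (arcsine), 0.673 (null variance) and 0.677 (continuity-corrected). None gives 0.679 together with the other five entries.

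**Step 3: the primary outcome on its own base (N = 95, m = 1.5).** At ICC 0.03, D = 1.015 and n = 47.5/1.015 = 46.8. For p0 = 0.50, p = 0.768: 7.849 × 0.4282/0.268² ≈ 46.8. For p0 = 0.80, p = 0.976. These are the 77% and 98% of section 4.8. Across ICC 0.01, 0.03 and 0.05 the rates are 0.767, 0.768, 0.769 and 0.975, 0.976, 0.976.

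**Step 4: the gap at ICC 0.03.**
- p0 = 0.50: 0.663 − 0.50 = 16.3 points on 315, against 0.768 − 0.50 = 26.8 points on 95.
- p0 = 0.80: 0.915 − 0.80 = 11.5 points on 315, against 0.976 − 0.80 = 17.6 points on 95.

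With 95 patients, power is about 37% for 0.663 against 0.50 and about 36% for 0.915 against 0.80.

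**Step 5: dependence on the study period.** The 315 is 35 per week × 9 weeks. Section 4.1 sets the formal period at 7 weeks, so 35 × 7 = 245 requests and 245 × 0.30 = 73.5 patients, or 73.5/63 = 1.17 per cluster. At ICC 0.03, D = 1.005 and n = 36.75/1.005 ≈ 36.6. The detectable rates become about 0.797 and 0.991.

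**The case against.** The appendix does not hide its base: 315, 63 and 5 stand directly above the rows, and five of the six proportions are right for it. It never names the primary outcome. The plan also has binary outcomes that are not confined to children without a recent weight (weight recorded within 30 days, first-touch resolution, refill prescribed), and the rows could be meant for those. Different sample sizes properly give different answers. Section 4.8 carries the correct 95-based figures and admits the limited power, and it does not use 0.663, 0.915 or 0.679.

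Most of this stands, and it limits the point. A reader might infer that the plan flatly contradicts itself, or that it claims more power for the primary outcome than it has. The documents do not support either reading, because the rows are unlabelled and the main text is right. A reader might also infer that 0.679 adds to the overstatement. It does the opposite: a larger detectable rate is less favourable than 0.668, and it sits at an ICC that section 4.8 does not use.

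What the objection does not remove is that section 4.8 powers none of those other binary outcomes, that the comparison rates are exactly those of Aim 1, and that the appendix lacks the one proportion calculation the main text relies on.

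**Conclusion.** The point holds as a fault in the power appendix, not in the design. The proportion rows rest on 315 requests, the 95-patient calculation is missing, and the rows are not labelled. If they are taken for the primary outcome, they understate the detectable difference by about 10.5 points at a comparison rate of 0.50 (26.8 − 16.3) and about 6 points at 0.80 (17.6 − 11.5). The 0.679 entry is too high by 0.011, possibly a typing slip, and errs on the safe side.

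The recalculation rests on the plan's own assumptions: 35 requests a week, 30% without a recent weight, equal clusters and 1:1 allocation. The 95-based values further assume nine weeks. Practical weight is small, because section 4.8 already states the right figures for that base.

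**What to change.** First reconcile the study period. Section 4.8 and Appendix A use nine weeks, and section 4.1 uses seven.

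Then add primary-outcome rows to Appendix A. On nine weeks (N = 95, cluster size 1.5) the entries for ICC 0.01, 0.03 and 0.05 are 0.767, 0.768, 0.769 at a comparison rate of 0.50, and 0.975, 0.976, 0.976 at 0.80. On seven weeks the ICC 0.03 entries are about 0.797 and 0.991, and the figures in section 4.8 must change to match.

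Either drop the 315-based proportion rows, or keep them with a label saying that they do not apply to the primary outcome, naming the outcome they serve, and with 0.679 corrected to 0.668. If they are kept and the period becomes seven weeks, recompute them too.

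The cost is a few table entries, with less favourable stated figures. Correcting the table requires no change to the randomization, outcome definitions or analysis model.
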